Remodulin in a neonate for the treatment of PPHN (11-13). In this case study, the subject was initiated at a dose of 1ng/kg/min of IV Remodulin and was titrated to a dose of 4ng/kg/min. Clinical response was noted within four days of initiation and down titration began after 10 days on therapy (11).

In children and adults, the most frequent AEs reported with Remodulin were related to the known pharmacological properties of treprostinil. These prostacyclin-related AEs are typically due to systemic effects that are characteristic of the prostacyclin class of medications (e.g., diarrhea, headache, nausea). To date, well over 10,000 patients, which includes over 1,000 pediatric patients (<12 years of age) and study subjects have been exposed to Remodulin for more than 11 years.

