3.3 CLINICAL ASSESSMENTS

3.3.1 *Efficacy*

3.3.1.1 *Assessment of Clinical Worsening*

Efficacy will be assessed by a composite primary endpoint of clinical worsening assessed at Day 14 or hospital discharge, whichever comes first, as defined by one of the following events:

- Death
- Initiation of ECMO per institutional policies
- Need for additional treatment (initiation of additional targeted pulmonary vasodilator therapy for PPHN)

Clinical worsening will be evaluated from Baseline (initiation of study drug) to the time of discontinuation of study drug, discharge from the hospital, or at the conclusion of Day 14, whichever comes first. Events occurring after the first 14 days of treatment will not count towards the primary endpoint.

3.3.1.1.1 *Need for Additional Treatment*

The following criteria should be met prior to initiation of additional targeted pulmonary vasodilator therapy for PPHN (all criteria required):

- OI measurement >20
- In the clinical judgment of the Investigator, subject requires addition of another targeted pulmonary vasodilator therapy (e.g., PDE-5i, ERA, alternate prostanoid [epoprostenol, iloprost], L-citrulline) due to worsening of clinical status or unsatisfactory clinical response
- Subject has received study drug for at least 24 hours and reached a minimum dose of 10ng/kg/min, or is unable to tolerate further increases (e.g., due to systemic hypotension); **OR**
 - If less than 24 hours, subject has two consecutive OI measurements >30 separated by at least one hour **OR** two consecutive arterial lactate levels of $\geq 4\text{mmol/L}$ separated by at least one hour

If an additional pulmonary vasodilator therapy is added after Day 14, the subject will not meet the primary endpoint definition of clinical worsening.

3.3.1.1.2 *Extracorporeal Mechanical Oxygenation (ECMO)*

ECMO will be initiated per institutional policy. Any subject who initiates on ECMO during the first 14 days of the study will meet the definition of clinical worsening. The initiation of ECMO after Day 14 will not be considered a clinical worsening event for the purposes of the primary endpoint of the study.

3.3.1.1.3 *Death*

Any subject who dies within the first 14 days of the study will meet the definition of clinical worsening. Deaths that occur after Day 14 will not be considered a clinical worsening event for the purposes of the primary endpoint of the study.

All deaths will be reported as a serious adverse event (SAE) (Section 9).

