3.3.1.2 *Oxygenation Index (OI)*

The OI is an assessment of how much oxygen diffuses across the membranes of the lungs and into the blood when a subject inhales. Higher OIs indicate an increased risk of poor subject outcomes because the subject is unable to get as much oxygen out of each breath. Typically when the OI is greater than 40, ECMO is considered. The OI is calculated as follows:

$$OI = [MAP(\text{mmHg}) \times \text{FiO}_2(\%) / \text{PaO}_2(\text{mmHg})] \times 100$$

An OI will be calculated at Screening, Baseline, approximately every 6 hours for the first 72 hours, daily starting on the fourth day of study drug for as long as the subject is on study drug, and within 1 hour prior to weaning study drug for as long as the subject has arterial access for collection of arterial blood gases (ABGs) and is on mechanical ventilation (Table 3-1). An OI will be collected on study Day 7 and Day 14 (as long as the subject has arterial access for collection of ABGs and is on mechanical ventilation) regardless if the subject has already been weaned from study drug.

The OI should be used to guide study drug dosing. When the OI cannot be calculated (i.e., no arterial access for ABGs and/or subject not on mechanical ventilation), FiO_2 will be used to guide dosing (per Section 6.1.3).

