4.3 PRESCRIBED THERAPY

4.3.1 *Concomitant Medications*

All subjects will be concurrently receiving iNO prior to randomization. Subjects should be adequately treated (as determined by the Investigator) with standard of care treatments for PPHN (e.g., inotropes, opioids, sedation) prior to enrollment and during the study. Doses of medications should be adjusted as needed during the study. All concomitant medications will be recorded in the subject's eCRF up until 48 hours after discontinuation of study drug. Any concomitant medications used in the treatment of an AE or SAE will be recorded even if it occurs more than 48 hours after discontinuation of study drug.

Caution should be used with cytochrome P450 (CYP) 2C8 enzyme inducers/inhibitors, such as rifampin or gemfibrozil, as plasma concentrations of treprostinil may be altered. Concomitant administration of Remodulin with diuretics, antihypertensive agents or other vasodilators may increase the risk of symptomatic hypotension. Remodulin inhibits platelet aggregation, there may be an increased risk of bleeding when administered with other anticoagulants, such as warfarin, heparin, or NSAIDs.

4.3.1.1 *Inotropic Dose Changes*

Doses of inotropic and vasoactive agents (e.g., dopamine, epinephrine, dobutamine, milrinone, vasopressin, norepinephrine) will be recorded with each dose change of study drug.

4.3.1.2 *Initiation of a Pulmonary Vasodilator Therapy*

If the Investigator initiates a targeted pulmonary vasodilator (after meeting the requirements outlined in Section 3.3.1.1.1) during the first 14 days after randomization, the subject will meet the definition of the primary endpoint of clinical worsening.

Subjects randomized to study drug who meet the definition of clinical worsening may continue to receive study drug for a total of up to 28 days at the discretion of the Investigator.

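### The additional-treatment component of the primary endpoint needs an OI that some infants no longer have, and the protocol and SAP disagree on whether a vasodilator start in them counts

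*Protocol*

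**What the plan says.** Clinical worsening through Day 14 has three components: death, ECMO and need for additional treatment. For the third, protocol 3.3.1.1.1 states: "The following criteria should be met prior to initiation of additional targeted pulmonary vasodilator therapy for PPHN (all criteria required". The criteria are:

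- "OI measurement >20";
- the investigator's judgment that another targeted agent is needed;
- either "Subject has received study drug for at least 24 hours and reached a minimum dose of 10ng/kg/min, or is unable to tolerate further increases", or, earlier than that, the alternative that begins "If less than 24 hours, subject has two consecutive OI measurements >30 separated by at least one hour" and also admits two raised arterial lactates.

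Protocol 3.3.1.2 describes "When the OI cannot be calculated (i.e., no arterial access for ABGs and/or subject not on mechanical ventilation" and uses FiO2 for dosing in that case. Table 3-1 footnote e likewise limits OI to ventilated infants with arterial gases.

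On scoring, the texts differ:

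- Protocol 4.3.1.2 says that a start in the first 14 days is clinical worsening "after meeting the requirements outlined in Section 3.3.1.1.1". Section 2.1 cross-refers to the same criteria.
- Protocol 10.3.1 and SAP 2.1 describe the component as initiation of another targeted pulmonary vasodilator, with no OI or dose condition.
- SAP 10.2.5 takes worsening status from the eCRF worsening page, and SAP 8.3.1 scores a missing status as an event.

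On the window, protocol 3.3.1.1 evaluates worsening from Baseline "to the time of discontinuation of study drug, discharge from the hospital, or at the conclusion of Day 14, whichever comes first". Table 3-1 footnote j and section 10.3.1 run to Day 14 or discharge, with no stop at drug discontinuation.

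**The concern.** Infants without a calculable OI are expected: the protocol plans for them in dosing. If such an infant deteriorates and is started on a further vasodilator before Day 14, a strict reading of 3.3.1.1.1 cannot be satisfied at that moment. Under 4.3.1.2 the infant is then scored as not having worsened; under 10.3.1 and SAP 2.1 the same infant has worsened. Nothing says whether an uncalculable OI means not met, not applicable or missing.

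The endpoint is binary with a planned 33 infants per arm, so a few reclassified infants can matter. Infants without an OI are likely to include those who had improved enough to lose the ventilator or the arterial line. If treprostinil brought that about sooner, unscorable starts would gather on the active arm and the comparison would lean towards the drug.

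**Working it through.** **1. The plan's own figure.** Inputs (protocol 10.2, SAP 5): 60% vs 30%, one-sided alpha 0.05, 80% power. The mean rate is 0.45.

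n per arm = [1.645·√(2·0.45·0.55) + 0.842·√(0.6·0.4 + 0.3·0.7)]² / 0.30² = [1.157 + 0.565]² / 0.09 = 32.9, so 33 per arm and 66 in total. The stated size reproduces. Exact power of the Pearson chi-square test at 33 per arm is 81.2% one-sided at 0.05 and 73.6% two-sided at 0.05. The two-sided test is used below because it is the SAP section 8 default and matches the hypothesis in SAP 10.1.1.1.

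**2. The texts side by side.**

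| Infant when a further vasodilator is started, by Day 14 | 3.3.1.1.1 criteria | Under 4.3.1.2 | Under 10.3.1 / SAP 2.1 |
|---|---|---|---|
| OI above 20; at least 24 h on drug; reached 10 ng/kg/min or cannot tolerate more | Met, given investigator judgment | Event | Event |
| Off the ventilator or no arterial access | No current OI, no substitute | Not counted | Event |
| OI above 20; at least 24 h; tolerating; never reached 10 ng/kg/min | Dose condition not met | Not counted | Event |
| Already off study drug | Depends on OI and on the dose reached | Outside the 3.3.1.1 window | Inside the window |

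Sections 3.3.1.1.2 and 3.3.1.1.3 count ECMO or death in the first 14 days with no OI or dose condition.

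**3. How often the dose condition should bite.** Section 6.1.3 starts at 1 ng/kg/min and allows increases of up to 2 ng/kg/min every 2 hours. The distance to 10 is 9 ng/kg/min.

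- Steps of 2: 5 increases, 10 hours.
- Steps of 1: 9 increases, 18 hours.
- Steps of 0.5 (assumed): 18 increases, 36 hours; the dose at 24 hours is 1 + 12 × 0.5 = 7.

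So the third row should be uncommon and arises mainly with slow titration.

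**4. Size, by assumption.** Let the true event rate be 60% in both arms, s the share of events that are additional-treatment starts, and u the fraction of those starts that is unscorable. The scored rate is 0.60 × (1 − s·u). For s = 50% and u = 30% it is 0.60 × 0.85 = 51.0%. The last column is the exact probability, from binomial enumeration, that the two-sided chi-square test rejects in the drug's favour.

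| Unscorable, drug vs placebo | s | Scored rates, drug vs placebo | False finding for drug |
|---|---|---|---|
| 0% vs 0% | – | 60.0% vs 60.0% | 3.0% |
| 10% vs 5% | 50% | 57.0% vs 58.5% | 4.0% |
| 30% vs 10% | 30% | 54.6% vs 58.2% | 5.8% |
| 30% vs 10% | 50% | 51.0% vs 57.0% | 8.5% |
| 50% vs 20% | 30% | 51.0% vs 56.4% | 7.8% |
| 50% vs 20% | 50% | 45.0% vs 54.0% | 13.1% |

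Reversing the imbalance (10% on drug, 30% on placebo) lowers the figure to 1.5% (s = 30%) or 0.9% (s = 50%).

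**5. Equal loss.** If 30% of starts are unscorable in both arms, 60% vs 30% becomes 54.6% vs 27.3% (s = 30%) or 51.0% vs 25.5% (s = 50%). Two-sided power falls from 73.6% to 65.7% or 60.1%; one-sided power falls from 81.2% to 74.7% or 70.0%.

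**The case against.** A reader might infer that extubated, line-less, weaned or low-dose infants cannot score this event however ill they are. The documents do not support that:

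- The dose condition is that 10 ng/kg/min was reached, so a past dose satisfies it during weaning. Intolerance of further increases is an alternative, and before 24 hours no dose is required.
- A responder with a low peak dose is not shut out for good. The background case "was titrated to a dose of 4ng/kg/min", but under 6.1.3 an infant still on study drug whose OI is 15 or more is to be up-titrated, and so either reaches 10 or shows intolerance. For an infant fully off drug, the first obstacle is the discontinuation cut-off in 3.3.1.1.
- A re-intubated infant with arterial gases has an OI again.
- Death and ECMO still count.

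The 24-hour switch also looks worse than it is. Identical severe OIs can qualify at hour 23 and fail at hour 25, but only in an infant who tolerates study drug and has been titrated slowly. Asking for adequate exposure first, with an early exception for severe cases, is a coherent choice. Few infants should lack an OI in the first 24 hours, because those expected to be ventilated for under 48 hours are excluded.

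The strongest objection is that the criteria are worded as what should be met, the OI criterion has no time window, and no sentence says that a start outside the criteria is a non-event. If initiation alone counts, there is no bias. That stands, and it is why the point is a conflict between texts rather than a proven scoring error. It does not remove the need to settle which text governs.

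**Conclusion.** The point holds as a scoring conflict in one component of the primary endpoint. Section 3.3.1.1.1 offers no route when OI is not calculable, 4.3.1.2 makes the endpoint depend on that section, and 10.3.1 and SAP 2.1 do not. The dose condition creates the same conflict in what should be a small group. The two evaluation windows create another for infants already off study drug.

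It is tempting to conclude that the rule favours treprostinil. That is possible but not shown. The documents give neither the share of additional-treatment starts among events nor the unscorable fraction in either arm. The intolerance route may also open more often on active drug, for example through hypotension, which would make drug-arm starts easier to score. The rise from 3.0% to between 4.0% and 13.1% rests wholly on the assumed fractions, with more loss on drug; with the imbalance reversed the figure falls below 3.0%.

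This should be corrected before unblinding: the change is inexpensive, and afterwards any choice between the readings would be made with the results in view.

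**What to change.** - In the SAP primary endpoint definition, state that any start of a targeted pulmonary vasodilator for PPHN from Baseline through Day 14 or discharge, whichever comes first, counts as clinical worsening. Include starts when OI was not calculable and starts after study drug was weaned or stopped.
- Align the scoring language in protocol 3.3.1.1 (including its stop at drug discontinuation) and 4.3.1.2 with this.
- At the blinded data review already planned in SAP 6, list every start that does not meet 3.3.1.1.1, with the reason.
- Add a sensitivity analysis that counts only criteria-met starts. Report it whatever the primary result, since SAP 10.1.1.3 otherwise runs sensitivity analyses only after a significant one.
- Ask the sponsor and investigators to reconcile the branches of 3.3.1.1.1 before and after 24 hours. No threshold or dose is proposed here.

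The cost is a protocol clarification, a few SAP sentences, a short case list and one extra table. The real downside is that some events will rest on blinded investigator judgment without an OI value; the criteria-met analysis shows how much the result depends on them.

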3.3.1.3 Mean Airway Pressure (MAP)

The MAP is the mean pressure applied during positive-pressure mechanical ventilation (standard or high frequency) and will be recorded while the subject is mechanically ventilated at Screening, Baseline, approximately every 6 hours for the first 72 hours, daily starting on the fourth day of study drug for as long as the subject is on study drug, within 1 hour prior to weaning/discontinuing study drug, every 24 hours while weaning, and at the time of discontinuation of study drug. The MAP will be recorded on study Day 7 and Day 14 (as long as the subject is on mechanical ventilation) regardless if the subject has already been weaned from study drug.

3.3.1.4 Fraction of Inspired Oxygen (FiO₂)

The FiO₂ and route of delivery will be assessed at Screening, Baseline, every 6 hours for the first 72 hours, daily starting on the fourth day of study drug for as long as the subject is on study drug, within 1 hour prior to weaning/discontinuing study drug, every 24 hours while weaning, and at the time of discontinuation of study drug. The FiO₂ and route of delivery will be recorded on study Day 7 and Day 14 regardless if the subject has already been weaned from study drug. Additionally, FiO₂ will be collected with each study drug dose change.

When OI is no longer calculated (i.e., no arterial access for ABGs), FiO₂ will be used to guide study drug dosing. The dose of study drug should be increased in the absence of dose-limiting AEs (e.g., hypotension) if the FiO₂ is $\geq 60\%$. When the FiO₂ is less than 60%, weaning of study drug can begin (see Section [6.1.4](#)).

3.3.1.5 Blood Gas and Lactate

Blood gas (arterial, capillary, or venous) values will be collected at Screening, Baseline, every 6 hours for the first 72 hours, then daily starting on the fourth day of study drug for as long as the subject is on study drug. Additionally, blood gases will be assessed within 1 hour prior to weaning and at the time of study drug discontinuation. Blood gases will be assessed on study Day 7 and Day 14 regardless if the subject has already been weaned from study drug.

The ABGs should be collected from a post-ductal artery when possible. If a post-ductal arterial catheter is not available, it should be noted in the eCRF that the ABG was collected from a pre-

ductal artery. The ABGs will include: PaO₂, partial pressure of arterial carbon dioxide (PaCO₂), bicarbonate (HCO₃), oxygen saturation (SaO₂), and pH.

Capillary or venous blood gasses (CBGs or VBGs) will be collected when the subject no longer has arterial access. The CBG or VBGs will include: partial pressure of venous oxygen (PvO₂), partial pressure of venous carbon dioxide (PvCO₂), HCO₃, oxygen saturation (SvO₂), and pH.

Table 3-2 Blood Gasses

Blood Gasses	
Arterial	Capillary/ Venous
PaO ₂	PvO ₂
PaCO ₂	PvCO ₂
HCO ₃	HCO ₃
SaO ₂	SvO ₂
pH	pH

A blood lactate level will be collected with each blood gas.

3.3.1.6 Echocardiogram (ECHO)

Echocardiograms (ECHO) are used to rule out congenital heart defects and to assess the pulmonary artery (PA) and/or right ventricular (RV) pressures. Specifically, the following parameters will be recorded: tricuspid regurgitation (TR) jet velocity (if available); pulmonary regurgitation (PR) jet velocity (if available); direction of shunting through patent ductus arteriosus (PDA), atrial septal defect (ASD), ventricle septal defect (VSD) or patent foramen ovale (PFO) (if present); evidence and degree of RV dilation; and interventricular septal position.

An ECHO will be performed at Screening and repeated at Day 7 and Day 14, or prior to hospital discharge if that occurs prior to Day 14. Additionally, an ECHO will be performed prior to weaning study drug and within 48 hours of study drug discontinuation.

3.3.1.7 N-Terminal pro B-Type Natriuretic Peptide (NT-proBNP)

NT-proBNP is a cardiac biomarker associated with volume or pressure overload of the right ventricle. Subjects will have samples for NT-proBNP collected at Baseline, daily during the first 72 hours of study drug treatment, Day 7, and at Day 14, or prior to hospital discharge if that occurs prior to Day 14. Additionally, subjects will have samples collected for NT-proBNP prior to weaning study drug and at the time of study drug discontinuation.

3.3.2 Safety

3.3.2.1 Physical Examination

A physical examination will be conducted at Screening, Baseline, daily during the first 72 hours of study drug treatment, on Day 7, and Day 14. Additionally, subjects will have a physical examination prior to weaning study drug, within 24 hours of study drug discontinuation, and prior to hospital discharge, or at 4 weeks after discontinuing study drug, whichever comes first. Length and weight will be collected at Baseline and at the final follow-up visit. The Baseline weight will be used to calculate all doses of study drug.

3.3.2.2 Vital Signs

Vital signs will include blood pressure (BP), heart rate (HR), respiratory rate (RR), temperature (temp), and oxygen saturation (SpO₂). Both pre- and post-ductal SpO₂ will be collected for the first 72 hours. Vital signs will be collected at Screening, Baseline, and during study drug administration as follows: approximately every 6 hours for the first 72 hours, daily starting on the fourth day for as long as the subject is on study drug, prior to weaning, every 24 hours while weaning, at the time of study drug discontinuation, and 48 hours after study drug discontinuation. Vital signs will also be collected prior to hospital discharge or at the 4 week follow-up after discontinuing study drug, whichever comes first. Additionally, BP, HR, and SpO₂ will be collected with each study drug dose change.

3.3.2.3 Clinical Laboratory Assessments

3.3.2.3.1 *Chemistries, Hematology and Liver Function Tests*

A complete metabolic, hematologic, and liver function panel will be assessed at Baseline, Day 7, and Day 14. Additionally, subjects will have clinical laboratory assessments prior to weaning study drug, within 12 hours of study drug discontinuation, 48 hours after discontinuing study drug, and prior to hospital discharge or at the 4 week follow-up after discontinuing study drug, whichever comes first. [Table 3-3](#) summarizes each laboratory parameter to be assessed.

Table 3-3 Chemistries, Hematology and Liver Function Tests

Chemistries	Hematology	Liver Function Tests (LFTs)
Sodium Potassium Chloride Bicarbonate/ CO ₂ Blood Urea Nitrogen (BUN) Creatinine Glucose Calcium Albumin Lactate ^a	Red Blood Cell Count Hematocrit Hemoglobin Platelet Count White Blood Cell Count (no differential) Prothrombin time	Alkaline Phosphatase Alanine Aminotransferase (ALT) Aspartate Aminotransferase (AST) Total Bilirubin

^aSee Section [3.3.1.5](#)

3.3.2.4 Adverse Events (AEs)

Documentation of AEs will be recorded in the eCRF from the time informed consent is provided until time of screen failure, time subject is withdrawn from study, time of hospital discharge, death, or until 4 weeks after the last dose of study drug, whichever comes first. All AEs should be followed until either resolution (or return to normal or Baseline values), until judged by the Investigator to no longer be clinically significant or until 4 weeks after last dose of study drug. Subjects with ongoing AEs at the time of hospital discharge will continue to be followed for their AEs until either resolution (or return to normal or Baseline values), until judged by the Investigator to no longer be clinically significant, or until 4 weeks after last dose of study drug. All SAEs will be followed until resolution, death, or the subject is lost to follow-up, even if they are ongoing more than 4 weeks after the last dose of study drug. Sections [9](#) and [15.1](#) provide the definitions and guidelines for recording AEs. If the subject receives Remodulin after hospital discharge, beyond Day 56/End of study, or following withdrawal from the study, AEs/SAEs will be subject to AE/SAE reporting under local government post-marketing AE/SAE reporting requirements.

